2. LIST OF ABBREVIATIONS

Abbreviation	Definition
AA	Alopecia Areata
BMI	Body Mass Index
CPRD	Clinical Practice Research Datalink
DSP	Data Security and Protection
EMA	European Medicines Agency
ENCePP	European Network of Centres for Pharmacoepidemiology and Pharmacovigilance
EQUATOR	Enhancing the QUAlity and Transparency Of health Research
ESA113	Employment Support Allowance
GEP	Good Epidemiological Practice
GP	General Practitioner
GPP	Good Pharmacoepidemiology Practices
IB113	Incapacity benefit
ICD10	International Statistical Classification of Diseases and Related Health Problems 10th Revision
IEA	International Epidemiological Association
IMD	Index of Multiple Deprivation
ISPE	International Society for Pharmacoepidemiology
ISPOR	Pharmacoconomics and Outcomes Research
NHS	National Health Service
OPCRD	Optimum Patient Care Research Database
RCGP RSC	Royal College of General Practitioners Research and Surveillance Centre

SAP	Statistical Analysis Plan
SD	Standard Deviation
SES	Socioeconomic Status
THIN	The Health Improvement Network
UK	United Kingdom
US	United States

4. ABSTRACT

Report title:

Healthcare disparities in alopecia areata: UK population-based cohort study

Version:

1.0

Protocol date: 02 November 2022

Main author: [name], Pfizer Ltd.

Rationale and background:

Alopecia areata (AA) is a common, immune-mediated non-scarring form of alopecia. Our previous work has provided the most comprehensive analysis of the epidemiology of AA to date. We found that AA is more common in people of lower socioeconomic status and in people from Black, Asian, and mixed ethnic groups compared to those of White ethnicity. However, these data formed a small component of the initial study and there is substantial scope to expand on these initial data to provide a greater understanding of the total disease burden across these groups including reporting lifetime risk estimates.

Research question and objectives:

The overall purpose of the study is to provide an estimate of the cumulative lifetime incidence of AA in the population overall and by (important) sociodemographic groups. Moreover, to do a subgroup analysis in the AA population to identify health-related disparities across people in different socioeconomic strata, geographical distribution, sex and ethnic groups.

Study Design:

The study will use retrospectively collected anonymised data from all eligible patients in the Oxford-Royal College of General Practitioners (RCGP) Research and Surveillance Centre (RSC) dataset at the date of data extraction. A cross-sectional design (incidence) will be used to assess the total disease burden of AA, stratified by sociodemographic groups. A matched-cohort design will be used for incidence of AA related: Mental health conditions; work impact; healthcare utilisation.

Population:

The cohort for this study will consist of all adults and children (aged 12+) contributing to RCGP RCS database during the study period (between January 1, 2009 and December 31, 2018 inclusive). People diagnosed with AA will be identified using diagnosis codes specific to the condition.

Variables:

Exposure: People diagnosed with AA as defined by clinical diagnosis codes.

Outcomes: For the impacts of AA on different sociodemographic groups assessment outcomes will comprise: incidence of AA, depressive episodes, recurrent major depression, anxiety disorders, dermatology referrals, primary care visits, referrals for psychological therapy, psychiatric reviews, time off work for illness and unemployment.

Covariates: Three different adjustment sets will be used for each endpoint analysis. These include: an unadjusted model, a sex and age adjusted model, and a multivariable model with an adjustment set of: body mass index (BMI), smoking status, alcohol use, and common comorbidities: type 2 diabetes, hypertension, atrial fibrillation, angina, acute myocardial infarction, stroke, heart failure, chronic liver disease, dementia, rheumatoid arthritis, asthma, chronic obstructive pulmonary disease, chronic kidney disease, malignancy and inflammatory bowel disease.

Data sources:

The RCGP RSC is the longest running primary care network in the UK, collecting weekly data since 1964. The RCGP RSC database contains complete data on all events and clinical entities coded in UK primary care.

Study size:

The RCGP RSC cohort is drawn from a large GP practices network across England, currently covering a registered population of 2.6 million people, representing a broadly representative sample of the UK.

Data Analysis:

Cumulative lifetime incidence of AA will be estimated using cases of incident AA occurring during the observational study period (January 1, 2009 and December 31, 2018). For all analyses, the overall results including both adults (aged 18+) and children (aged 12-17) will be published, with stratification by sex, ethnicity, deprivation quintile, geographic region and urban/rural classification. The assessment of any associations with baseline characteristics and the outcomes of interest will be assessed using Cox proportional hazards models (time to event outcomes) and Poisson regression (repeated event outcomes) models. Three different adjustment sets will be used for each endpoint analysis.

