8. RESEARCH QUESTION AND OBJECTIVES

8.1. Study Objectives

The overall purpose of the study is to provide an estimate of the cumulative lifetime incidence of AA in the population overall and by sociodemographic groups (sex, ethnicity, deprivation, geographic location and urban-rural status). Moreover, to perform a subgroup analysis in the AA population to identify health-related disparities across people in different socioeconomic strata, geographical distribution, sex and ethnic groups. The disparities that will be considered are AA associated: Mental health conditions; healthcare utilisation; and work impact (time off work and unemployment).

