8.3. Secondary Objectives

8.3.1. Objective 4

Describe any disparities in AA related work impact (time off work and unemployment) across sociodemographic groups.

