9.2.2. Sociodemographic subgroups

Age, sex, socioeconomic status, ethnicity, major regions of England and urban/rural classification will comprise the sociodemographic factors used for stratification of the outcome measures.

Ethnicity will be grouped using the standardised definitions of major UK ethnic groups: Black, Asian, White mixed, and others.¹³

Socioeconomic status (SES) will be defined using the national deprivation measure; index of multiple deprivation (IMD) and stratified into quintiles of deprivation according to the national distribution.¹⁴ IMD is calculated at the point of data extraction, using patient postcode.

Age will be stratified into four age categories: children aged 12-17, 18-29, 30-49 and 50+ based on our previous research into incidence of AA.²

Geographical distribution will consist of two subgroups including; geographic region and urban/rural classification. Geographic region within England comprises; Greater London, South East, South West, West Midlands, North West, North East, Yorkshire and the Humber, East Midlands, and East of England.

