9.2.3. Inclusion criteria

Patients must meet all of the following inclusion criteria to be eligible for inclusion in the study:

1. The cohort for this study will consist of all adults and children (aged 12+) contributing to RCGP RCS database during the study period (between January 1, 2009 and December 31, 2018 inclusive).
2. The AA population consists of patients newly diagnosed with AA at any point during the study period.

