9.2.4. Exclusion criteria

Patients meeting any of the following criteria will not be included in the study:

1. People with the alternative non-AA diagnoses (section 9.2.1).
2. People with AA diagnosis within 6 months of registration.
3. People with less than 1 year of follow up within the dataset.
4. People over the age of 95.

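### Objective 4 sets no working-age analysis population, so overall unemployment and time-off-work rates understate impact among people who could be working, and unadjusted group comparisons can partly reflect age mix

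*Combined protocol and SAP*

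**What the plan says.** Objective 4 (8.3.1) is to "Describe any disparities in AA related work impact (time off work and unemployment) across sociodemographic groups". Its endpoints are defined in 9.3 and 9.5 by unemployment codes or incapacity and employment-support forms, and by fitness-for-work (Med 3) certification, over two years. Neither definition sets an age or labour-market condition.

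The cohort in 9.2.3 is "all adults and children (aged 12+) contributing to RCGP RCS database during the study period". The only upper age limit, in 9.2.4, excludes "People over the age of 95". Section 4 and 9.1 then say "For all analyses, the overall results including both adults (aged 18+) and children (aged 12-17) will be published". The strata planned for these results follow in the same sentence: "with stratification by sex, ethnicity, deprivation quintile, geographic region and urban/rural classification".

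Age is handled in several places:

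- 9.2.2: "Age, sex, socioeconomic status, ethnicity, major regions of England and urban/rural classification will comprise the sociodemographic factors used for stratification of the outcome measures". The bands are "children aged 12-17, 18-29, 30-49 and 50" and over, so the last one is open up to the age limit of 95.
- 9.3 gives age and sex the roles of baseline characteristic, subgroup variable and potential confounder.
- Section 4 and 9.1 plan three models per endpoint: unadjusted, adjusted for sex and age, and multivariable. The form of age is not given, and the written multivariable list names neither age nor sex.
- The strata in section 4 and 9.1, and the groups in 8.1, "sociodemographic groups (sex, ethnicity, deprivation, geographic location and urban-rural status", do not include age.

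**The concern.** The work endpoints are labour-market events. Schoolchildren and most retired people have little or no chance of one, yet they count in the overall denominator. Two consequences follow.

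First, an overall rate or risk difference is lower than the one among people of working age, by an amount that depends on how many are outside that range.

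Second, Objective 4 compares ethnic, deprivation, regional and urban/rural groups. If two groups have the same working-age risk but different shares of working-age people, an unadjusted comparison shows a disparity that is only age mix. Age adjustment removes this only as far as it separates people who could be working from those who could not. A single band from 50 to 95 does not.

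**Working it through.** The documents give no rate, denominator or sample size for Objective 4, and 9.7.1 covers only anxiety and depression. There is no planned figure to reproduce, so everything below is an illustration on assumed inputs.

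**Assumptions.** Working age is 18-64. Risk is 20% at 18-64 in both groups and 0 outside, so the true ratio is 1.00. Shares at 12-17 / 18-29 / 30-49 / 50-64 / 65-95 are 5/35/35/20/5% in group 1 and 5/32/33/20/10% in group 2, with ages uniform within each band. Working-age shares are then 35+35+20 = 90% and 32+33+20 = 85%. A mild contrast was chosen because section 7 puts peak incidence at 25-29, which suggests that many cases are of working age.

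**Dilution.** Overall risk = working-age share × working-age risk.

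- Group 1: 0.90 × 20% = 18%. Group 2: 0.85 × 20% = 17%.
- A 5-point working-age risk difference becomes 0.90 × 5 = 4.5 or 0.85 × 5 = 4.25 points.

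**Crude ratio between groups.** 0.18 / 0.17 = 1.059.

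**Adjusted for the four bands of 9.2.2.** In a Poisson model with band and group terms, the group ratio θ solves Σ E × n1θ/(n1θ + n2) = 0.18. Here E is the expected events in the band over both groups, n1 and n2 are the band shares, and 0.18 is the group 1 total.

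- 12-17: no events.
- 18-29: E = 0.20 × (0.35 + 0.32) = 0.134.
- 30-49: E = 0.20 × (0.35 + 0.33) = 0.136.
- 50+: E = 0.20 × (0.20 + 0.20) = 0.080, with n1 = 0.25 and n2 = 0.30.
- At θ = 1.043: 0.134 × 0.533 + 0.136 × 0.525 + 0.080 × 0.465 = 0.0714 + 0.0714 + 0.0372 = 0.180.

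The residue comes entirely from the open band. Within 50+ the risks are 0.20 × 20/25 = 16.0% and 0.20 × 20/30 = 13.3%. Within 18-29 and 30-49 the ratio is 1.00.

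**Other forms of age, same inputs:**

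| Analysis | False ratio |
|---|---|
| Unadjusted | 1.059 |
| Linear age | 1.043 |
| Four bands | 1.043 |
| Quadratic in age | 1.013 |
| Five-year bands | 1.002 |
| Restricted to 18-64 | 1.000 |

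**Sensitivity.** With 1% rather than 0 risk outside 18-64, the crude ratio is (0.90 × 0.20 + 0.10 × 0.01) / (0.85 × 0.20 + 0.15 × 0.01) = 0.181 / 0.1715 = 1.055. Four bands give 1.040 and five-year bands 1.002.

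Restriction returns exactly 1.000 only because risk was set equal across 18-64. If risk varied within that range, age adjustment would still be needed.

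**The case against.** The strongest reply is that the plan already deals with most of this. A sex- and age-adjusted model is planned for every endpoint, 9.2.2 makes age a stratification factor, and 9.3 names age and sex as subgroup variables and potential confounders. Any unadjusted estimate can reflect age mix, and here it would be read beside two others. Objective 4 only describes, an all-ages rate is a legitimate measure of population burden, and the documents define no working age. Section 9.9 leaves detail to a separate SAP, which may set denominators and the form of age.

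Much of this stands and limits the weight of the point. It does not answer two things. No model adjustment turns an overall rate at ages 12 to 95 into a measure of impact among people who could be working. And if the model uses the age categories of 9.2.2, the open 50+ band leaves part of the age difference in the estimate. The text available contains no working-age denominator.

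Stronger readings that a reader might infer are not supported:

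- That the plan ignores age, or that the multivariable model omits it. The list can be read as additions to the sex- and age-adjusted model, and 9.3 supports that reading. The wording needs clarifying; an omission is not established.
- That AA v non-AA ratios are biased. A matched cohort is planned for work impact (9.1.2). The matching variables are not stated, but with equal age mix these ratios are unaffected.
- That misleading group contrasts within 50+ will be published. Results by age band and sociodemographic group together are not stated as an output.
- That the distortion is large. A contrast of 90% v 70% would give 0.90/0.70 = 1.29 crude, but nothing in the documents supports such a gap.

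**Conclusion.** The point holds and is minor. As written, overall Objective 4 rates include people largely outside the labour market and cannot be read as work impact in people of working age. Unadjusted comparisons between sociodemographic groups can partly reflect age mix. The planned adjustment and strata reduce this without removing it, and the 18-29 and 30-49 strata are unaffected.

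The true size cannot be derived from the documents. On the assumed mild age mix, the overall rate is 10% to 15% lower in relative terms than the working-age rate, and the false group ratio is 1.06 crude and about 1.00 to 1.04 after age adjustment, depending on the form of age. The direction rests on work-related codes being rarer outside working age, which the endpoint definitions make likely but the documents do not quantify.

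A separate contradiction lends no weight to the above: 9.3 counts sick-leave codes or a Med 3 certificate as time off work, while 9.5 counts Med 3 only.

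**What to change.** In the protocol, or in the SAP that 9.9 refers to:

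1. Make a working-age analysis the main analysis for Objective 4, with bounds set and justified by the sponsor (for example 18 to 64 at index, with follow-up censored at the upper limit). Keep the all-ages result as supplementary; the sentence in section 4 and 9.1 does not prevent this.
2. For this objective, split the 50+ band at the chosen upper bound.
3. Adjust for age with a spline or five-year bands, and state that the multivariable model includes age and sex.
4. List age as a stratification factor in section 4, 8.1 and 9.1, as 9.2.2 does.
5. Separately, reconcile 9.3 and 9.5 to one definition of time off work.

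The cost is wording and one filter on data already extracted (9.8). The downsides are somewhat fewer patients in the main Objective 4 analysis, loss of the few workers outside the chosen ages, and a little more analysis work.

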5. AMENDMENTS AND UPDATES

None

6. MILESTONES

Milestone	Planned date
Start of data collection	25-October-2022
End of data collection	24-January-2023
Study progress report	29-November-2022
Final study report	21-February-2023

7. RATIONALE AND BACKGROUND

Alopecia areata (AA) is a common, immune-mediated non-scarring form of alopecia. Our previous work has provided the most comprehensive analysis of the epidemiology of AA to date¹. This study demonstrated that the incidence of AA is 0.26 per 1,000 person-years in the UK (United Kingdom), with a peak incidence at age 25-29; however incident AA occurs across the lifespan. We found that AA is more common in people of lower socioeconomic status and in people from Black, Asian, and mixed ethnic groups compared to those of White ethnicity². However, these data formed a small component of the initial study and there is substantial scope to expand on these initial data to provide a greater understanding of the total disease burden across these groups including reporting lifetime risk estimates. Current lifetime risk estimates are taken from a single population-based study with just 530 AA cases in a single region of the United States (US)³ and most reported age, sex and ethnicity prevalence estimates that have been produced from studies performed in secondary care⁴⁻⁸. These studies are likely to be missing a large proportion of cases and therefore substantially underestimate the total disease burden in these groups.

Our previous work strongly suggested there are significant socioeconomic and ethnic disparities in healthcare and outcomes in people with AA. A comprehensive assessment of these potential disparities in AA is needed, this would strongly complement the existing work and support the use of newer therapies in AA.

Our previous work has also demonstrated that AA is associated with significant psychological consequences including an increased incidence of depression and anxiety⁹. These data suggest a socioeconomic gradient in the mental health impacts of AA (with AA associated with a greater mental health burden in those with lower socioeconomic status). However, the study was not designed to assess this as a primary outcome, and further analysis is required to fully understand these potential relationships.

8. RESEARCH QUESTION AND OBJECTIVES

8.1. Study Objectives

The overall purpose of the study is to provide an estimate of the cumulative lifetime incidence of AA in the population overall and by sociodemographic groups (sex, ethnicity, deprivation, geographic location and urban-rural status). Moreover, to perform a subgroup analysis in the AA population to identify health-related disparities across people in different socioeconomic strata, geographical distribution, sex and ethnic groups. The disparities that will be considered are AA associated: Mental health conditions; healthcare utilisation; and work impact (time off work and unemployment).

8.2. Primary Objectives

8.2.1. Objective 1

Describe the total burden of AA (cumulative lifetime incidence) across sociodemographic groups (including geographical distribution).

8.2.2. Objective 2

Describe any disparities in AA related mental health conditions across sociodemographic groups.

8.2.3. Objective 3

Describe any disparities in AA healthcare utilisation across sociodemographic groups.

8.3. Secondary Objectives

8.3.1. Objective 4

Describe any disparities in AA related work impact (time off work and unemployment) across sociodemographic groups.

9. RESEARCH METHODS

9.1. Study design

The study will use retrospectively collected anonymised data from all eligible patients in the Oxford-Royal College of General Practitioners (RCGP) Research and Surveillance Centre (RSC) dataset at the date of data extraction. The cohort to be used for this study has already been specified for previous work as follows:

All adults and adolescents (aged 12+) registered with practices contributing data to RCGP RCS between January 1, 2009 and December 31, 2018, will be eligible for inclusion in the study. People who have opted out of record sharing will not be included (approximately 1.8% of the adult population) and have not been uploaded to the RCGP RCS database. Cumulative lifetime incidence of AA will be estimated using cases of incident AA occurring during the observational study period (January 1, 2009 and December 31, 2018). For all analyses, the overall results including both adults

(aged 18+) and children (aged 12-17) will be published, with stratification by sex, ethnicity, deprivation quintile, geographic region and urban/rural classification.

The assessment of any associations with baseline characteristics and the outcomes of interest (objectives 2-4) will be assessed using Cox proportional hazards models (time to event outcomes) and Poisson regression (repeated event outcomes) models. Three different adjustment sets will be used for each endpoint analysis. These include: an unadjusted model, a sex and age adjusted model, and a multivariable model with an adjustment set of: body mass index (BMI), smoking status, alcohol use, and common comorbidities: type 2 diabetes, hypertension, atrial fibrillation, angina, acute myocardial infarction, stroke, heart failure, chronic liver disease, dementia, rheumatoid arthritis, asthma, chronic obstructive pulmonary disease, chronic kidney disease, malignancy and inflammatory bowel disease.

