9.1.1. Total disease burden; cumulative lifetime incidence

A cross-sectional design (incidence) will be used to assess the total disease burden of AA, stratified by sociodemographic groups.

9.1.2. Disparities in the impact of AA on mental health, work impact and healthcare utilisation

A matched-cohort design will be used for incidence of AA related: Mental health conditions; work impact; healthcare utilisation.

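### Objective 1 is named a lifetime incidence, but a cohort entered at age 12 can estimate only incidence of AA from age 12; the start of time at risk also needs stating

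*Combined protocol and SAP*

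**What the plan says.** **The name.** Section 8.2.1 sets Objective 1 as: "Describe the total burden of AA (cumulative lifetime incidence) across sociodemographic groups (including geographical distribution". Section 9.1 adds: "Cumulative lifetime incidence of AA will be estimated using cases of incident AA occurring during the observational study period". Section 9.1.1 gives the design in one sentence: "A cross-sectional design (incidence) will be used to assess the total disease burden of AA, stratified by sociodemographic groups". Section 7 offers as a reason for the study "to provide a greater understanding of the total disease burden across these groups including reporting lifetime risk estimates", and states that "incident AA occurs across the lifespan".

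**The population.** Section 9.1 admits "All adults and adolescents (aged 12+) registered with practices contributing data to RCGP RCS between January 1, 2009 and December 31, 2018", and section 9.2.3 repeats the floor: "The cohort for this study will consist of all adults and children (aged 12+) contributing to RCGP RCS database during the study period". In section 9.2.2 the youngest age stratum is 12-17 and the oldest is open-ended from 50. Section 9.2.1 counts only first-ever AA codes within the study period and excludes people whose AA was diagnosed before it. Section 9.2.4 excludes people over 95 and people with under one year of follow-up.

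**The six-month rule.** Sections 9.2.1 and 9.2.4 both exclude people whose AA was diagnosed within six months of registration. Both are worded for people with an AA diagnosis. No section says when time at risk begins, what the denominator is, or which estimator produces the cumulative figure. Section 9.9 leaves detailed methods to a separate SAP, and section 9.1 says the cohort was specified for previous work. The supplied text contains neither.

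**The concern.** A lifetime incidence runs from birth. Here, a person with onset at age 8 is not observed as a case, because the cohort starts at 12. If that person is in the database later, they are removed for having AA before the study period. Childhood onset is therefore absent from both the cases and the people at risk. Since section 7 makes lifetime risk part of the rationale and sets it beside an earlier US lifetime estimate, readers will probably take the headline figure as a risk from birth and compare it as such.

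The six-month rule raises a separate question about the denominator. If early-diagnosed cases are dropped while everyone else's first six months still count as time at risk, cases leave the numerator without the matching time leaving the denominator, and the rate falls. The one-year minimum follow-up does not cure this, because people who meet it keep their first six months.

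**Working it through.** The plan gives no numerical target for Objective 1, so there is no figure to reproduce. The calculations below only illustrate size.

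**Inputs from the documents:** AA incidence 0.26 per 1,000 person-years (section 7); entry age 12 (section 9.1); cohort cap 95 (section 9.2.4); anticipated AA sample 6,007 (section 9.7.1, given there for the mental health comparison).

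**Assumptions:** a flat rate over age; death ignored; accumulation up to the cap of 95, which no section prescribes; an under-12 rate of *m* times the average; yearly list turnover *t*. The documents give neither *m* nor *t*.

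**1. Age floor.** Cumulative incidence = 1 - exp(-rate × years).

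- Ages 12-95: 1 - exp(-0.00026 × 83) = 2.13%
- Ages 0-95: 1 - exp(-0.00026 × 95) = 2.44%
- Difference: about 0.31 percentage points, or 12.5% of the 0-95 figure.

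For other under-12 rates, relative shortfall = 1 - [1 - exp(-0.00026 × 83)] / [1 - exp(-0.00026 × (83 + 12*m*))].

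| Assumed *m* | Shortfall |
|---|---|
| 0 | 0% |
| 0.25 | 3.5% |
| 0.5 | 6.7% |
| 1 | 12.5% |
| 1.5 | 17.6% |

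The last row is shown for completeness only. In this flat model it would make under-12s the highest-rate group, which sits badly with the peak at 25-29 reported in section 7.

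**2. Sampling error, for scale.** If the overall figure uses about 6,007 cases, its relative 95% half-width is 1.96/√6007 = 2.5%. The shortfall passes this once *m* exceeds about 0.18. Subgroup results are less precise. With an even split (assumed), a deprivation quintile has 6007/5 ≈ 1,201 cases and ±5.7%; one of nine regions has 6007/9 ≈ 667 cases and ±7.6%.

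**3. Six-month rule, if the time is kept.** Take a stationary list with exponential tenure and at least one year of follow-up. Mean tenure is then 1 + 1/*t* years, and the first half-year is 0.5/(1 + 1/*t*) = 0.5*t*/(1 + *t*) of person-time. That share is the downward bias.

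| Assumed *t* per year | Bias, formula | Bias, simulated 10-year window |
|---|---|---|
| 5% | 2.4% | 2.2% |
| 10% | 4.5% | 4.2% |
| 20% | 8.3% | 7.8% |
| 30% | 11.5% | 10.9% |

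A second approximation uses 0.5*f*/*T*, with *f* the share of people who register during the study and *T* the mean follow-up in years (both assumed). It gives 0.5% at *f* = 0.10, *T* = 10 and 12.5% at *f* = 0.50, *T* = 2. If the SAP removes the first six months for everyone, the bias is nil.

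**The case against.** The strongest reply on the label is that nothing is hidden. The 12+ limit appears in the abstract, the design, the strata and the inclusion criteria, so a reader can see which ages are covered, and no data or model would change. That is true and keeps the remedy small. But an eligibility rule does not qualify a result that is still called a lifetime figure, and the limitations section does not make the connection.

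On the six-month rule, the reply is that the protocol defines who counts as an incident case and is silent on person-time; silence does not show that the first six months are kept. This stands. The SAP or the earlier cohort specification may already trim everyone's time.

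The sizes also rest on assumed inputs. No document figure supports any particular under-12 rate or turnover, and the ±2.5% comparison belongs to the overall figure alone.

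Two stronger readings are tempting. A reader might infer that comparisons between sociodemographic groups are distorted; the documents do not show that childhood onset or turnover differs between groups. A reader might also infer that the published figure will be about 12.5% too low; that follows only if the under-12 rate equals the average, which the documents do not say.

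**Conclusion.** The label point holds on the text alone. With entry at 12 and earlier AA excluded, Objective 1 can estimate cumulative incidence of AA from age 12 among people with no earlier recorded AA, and not a risk from birth. This does not depend on any assumed rate. The size of the gap does: it is nil if there is no onset before 12, and about 0.31 percentage points (2.13% against 2.44%) if the under-12 rate equals 0.26 per 1,000, with a flat rate and death ignored.

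The six-month point is conditional. As worded, the rule is one-sided and the supplied text has no person-time rule, so a literal application would bias the rate downward. The documents do not establish that it will be applied that way, and they give no turnover from which to size the effect.

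The point should be fixed because it concerns the name of a primary result and costs little. Confidence is medium, since the methods documents that could settle the second part are not available.

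**What to change.** 1. In sections 8.2.1, 9.1 and 9.1.1, and where the term recurs in the abstract and section 8.1, rename the endpoint as cumulative incidence of AA from age 12 among people with no AA recorded before age 12. State the upper age to which incidence is accumulated; the cohort caps it at 95.
2. Add the age floor to section 9.11, noting that onset before 12 is not captured.
3. Unless the SAP or the earlier cohort specification already does so, state that time at risk starts for everyone, case or not, at the latest of 1 January 2009, the 12th birthday and registration plus six months.
4. As a check only, confirm that the SAP says how death is handled in the cumulative figure.

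**Cost.** Items 1 and 2 are wording, and the headline claim becomes narrower. Because this is a primary endpoint, section 9.9 may call for a protocol amendment. Item 3 is one rule applied to data already extracted; if the first six months are now being counted, person-time falls by about 2% to 12% over the assumed turnover range. Keeping the lifetime name would instead require a stated source of under-12 incidence, which the plan does not have.
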